Specific Aim #3:Establish the time needed to reach peak efficacy. Duration of treatment in the original study was three weeks, and significant therapeutic benefit was observed only at the three-week endpoint but not earlier. In the proposed study, subjects will receive study drug for 6 weeks and we expect that the size of the therapeutic benefit of oxytocin will increase from 3 to 6 weeks.

Specific Aim # 4: Investigate the possible cognitive effects of intranasal oxytocin. In the pilot study, oxytocin significantly improved short term recall performance in the California Verbal Learning Test. This raises the possibility that chronic oxytocin will improve cognitive deficits associated with schizophrenia. This study will test this hypothesis using the Computerized Multiphasic Interactive Neurocognitive DualDisplay™ System (CMINDS®) and Mayer-Salovey-Caruso Emotional Intelligence Test: Managing Emotions (MSCEIT™ ME).

Specific Aim #5: To determine if daily intranasal oxytocin is sufficiently safe, feasible and acceptable to patients to warrant further clinical development. Information derived from this study will inform development of oxytocin not only for schizophrenia but other potential neuropsychiatric disorders.

Specific Aim #6: The objective of the study is to compare the efficacy of intranasal oxytocin versus intranasal placebo to improve symptoms in schizophrenia patients who have residual symptoms despite being on adequate treatment with antipsychotic medication. Improvement will be measured by total score in the Positive and Negative Syndrome Scale (PANSS).

Specific Aim #7: To determine if oxytocin-induced enhancement of mu-rhythm suppression of 'mirror' neurons in schizophrenia patients can serve as a predictive biomarker of individual clinical response to this neurohormone.

Secondary objectives include:

 To evaluate the efficacy of intranasal Oxytocin as measured by change in the total CGI-Severity and Improvement scores

- To evaluate the efficacy of intranasal Oxytocin as measured by change in the total GAF score
- To evaluate the efficacy of intranasal Oxytocin as measured by change in the total scores of HAM-A.
- To evaluate the efficacy of intranasal Oxytocin on self-rated social anxiety as measured by change in the total Social Phobia Inventory (SPIN).
- To evaluate the efficacy of intranasal Oxytocin as measured by change in the total Calgary Depression Scale for Schizophrenia (CDSS) scores.

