thought to index the activity of 'mirror' neurons. Mu rhythms, measured from this brain region show reliable, dose dependent, suppression when the subject perceives biological motion (but not non-biological motion). Thus, mu wave suppression is an easily quantifiable operational measure of the neural processing of biological motion. In a recently published study conducted in [name] laboratory, the applicant showed that neural mu wave suppression induced by biological motion is impaired in first-episode of psychosis subjects, and that the neural impairment is inversely correlated with negative symptoms and social adjustment, providing construct validity for the mu suppression paradigm as an operational measure of social cognition in patients with psychosis (Singh, et,al, 2010).

Given OT's strong implication in social perception, it would be reasonable to expect that exogenous OT affects mu wave suppression in the context of biological motion. This has been in fact, confirmed in a recent study by Keri et al. using a well-established paradigm of biological motion similar to that used by our group. Keri et al, demonstrated that intranasal OT significantly enhanced detection of biological motion (human form) but not non-biological motion (rotating circle) compared to intranasal placebo. Taken together, the applicant's study and that by Keri et al, demonstrate that patients with psychosis have impaired biological motion induced mu suppression compared to normal subjects and that intranasal OT enhances this neural process in normal subjects. It is reasonable to expect that intranasal oxytocin will improve mu suppression in schizophrenia patients and we expect to demonstrate this. We also expect to find that subjects with the greatest enhancement in mu suppression are more likely to experience clinical improvement in response to 6-weeks of oxytocin treatment.

Hypothesis: We hypothesize that augmentation of antipsychotics with intranasal oxytocin will significantly improve psychopathology ratings as compared to placebo and an improvement in certain cognitive functions may be also observed.

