Mu wave suppression paradigm: If subjects agree to participate in this sub-study, the informed consent for EEG collection will be obtained prior to any EEG procedures. EEG waves will be recorded over 32-sites using a standard 32-electrode cap with the Biosemi system (9), while subjects are watching 60-80 second videos. The videos will consist of experimental conditions (point light animations of biological and non-biological motion, scrambled condition) and baseline condition (2 moving balls). All videos will be presented twice, using Presentation software (10). Data from both trials will be combined prior to analysis. Filters will be set to automatically identify and block any segments with eye movements and body movements (using +/- 40 microvolt deviations). Data will only be analyzed if there is at least 2 minutes of clean EEG per condition. For each segment, integrated power in the 8–13 Hz range will be computed using a Fast Fourier Transform. Mu suppression will be calculated for central (C3, Cz and C4) and occipital (O1 and O2) sites using the equation: Mu suppression = log10 (mu power of experimental condition/ mu power of ball condition). Occipital site electrical discharges will be recorded, integrated for power and compared between groups to determine if posterior alpha activity is causing differences across conditions.

STUDY PROCEDURES

Visit	Screen	Baseline	Midweek	3	4	5	6	7	8/ET
Week	-1	0	0	1	2	3	4	5	6
Days	-7 to -1	0	3/4	7	14	21	28	35	42
General Procedures									
Informed Consent	Х								
Assess Inclusion/Exclusion	Х	Х		Χ	Х	Х	Х	Х	Х
Medical History	Х								
Physical Exam	Х								
SCID/Psychiatric History	Х								
Urine Drug Screen ^b	Х								
Urine Pregnancy Screen ^c	Х	Х							
Vital signs/ weight	Х	Х		Χ	Χ	Х	Х	Х	Х
Blood chemistryd/Urine osmolality	Х								Х
Oxytocin Levels ^e		XX							Х
EEG	XX								Х

Clinician-Rated Scales									
PANSS ^f	(x)	Х		Х	Х	Х	Х	Х	Х
HAM-A/ CDSS/ CGI:S ⁹ /									
CGI:I/ GAF		Х		Х	Χ	Х	Х	Х	Х
Cognitive tests (CMINDS® and									Х
MSCEIT [™] ME) ^h	Х	Х							
Patient-Rated Scales									
CTQ	Х								
TSQM		Х		Х	Х	Х	Х	Х	Х
PTS/ SPIN/ ASEX ⁱ /									
ER-40/ ECR		XX		Х	Х	Х	Х	Χ	Х
Other Procedures									
Mid-Week Safety Call ^j			Х						
Dispense study drug		Х		Х	Х	Х	Х	Х	
Single Challenge Dose ^k	Х								
Concomitant Meds		Х	Х	Х	Х	Х	Х	Х	Х
Adverse Events		Х	Х	Х	Х	Х	Χ	Х	Χ
1-hr safety monitoring following in-									
clinic dose		Х							

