- If the volunteer is a woman capable of having children, a urine test will be done to ensure she is not pregnant
- Give a urine sample for testing to make sure there are no illegal or controlled substances in his/her body. The results of any urine drug screen will remain confidential and be disclosed only as required by law
- Blood draw (about one teaspoon or 5 mL) and urine sample will be collected that will include standard tests to make sure volunteers are healthy
- Be asked questions about health and any current illnesses or medications (including over-the-counter medications, herbal remedies, alcohol consumption, and substances of abuse).
 Be asked a series of questions about how s/he was feeling within the past few weeks such as whether there were anxious feelings, feelings of depression or difficulty concentrating. The volunteer will also possibly be asked about symptoms that are commonly associated with schizophrenia using a clinical interview called the SCI-PANSS (Structured Clinical Interview Positive and Negative Syndrome Scale).

The SCI-PANSS will be completed at the discretion of the investigator if he feels that the subject may not met entry criteria

- Complete a series of activities which will be used to measure process of thought called the CMINDS® and MSCEIT™ ME
- Premenopausal women will be queried regarding their menstrual cycles and data correlated with clinical findings
- Once all inclusion/exclusion criteria have been met subjects will have a baseline EEG performed
- Subsequently subjects will receive a, one time, challenge dose of 24 or 48 IU oxytocin followed by the EEG paradigm

Visit 2-Baseline (approximately 2 hours)

During Visit 2 – Baseline, the volunteer will:

- Have weight, pulse and blood pressure measured
- Be asked questions about health and any current illnesses or medications (including over-the-counter medications, herbal remedies, alcohol consumption, and substances of abuse)
- Be asked a series of questions about how s/he was feeling within the past few weeks such as whether
 there were anxious feelings, feelings of depression or difficulty concentrating. The volunteer will also be
 asked about symptoms that are commonly associated with schizophrenia using a clinical interview called
 the SCI-PANSS (Structured Clinical Interview Positive and Negative Syndrome Scale)
- Complete a series of activities which will be used to measure process of thought called the CMINDS® and MSCEIT™ ME

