PANSS scores, duration of illness, class of medication) will be tested using treatment-by-baseline characteristic interaction terms in the MMRM LDA and/or ANCOVA models. To assess impact of improvement in one domain (e.g. positive symptoms) on the efficacy of a related symptom domain (e.g. negative symptoms), a mediator analysis model with terms for treatment, baseline, and positive symptoms improvement will be applied to determine significance of oxytocin effect on reductions in negative symptoms after adjustment for potential positive symptom improvement. We will perform similar mediator analysis for assessing inter-relationships between cognitive improvement and symptom improvement in positive and/or negative symptoms. In addition, cross-sectional baseline and longitudinal change score associations between treatment outcome measures and mediator effects will be assessed by including mediators as time-varying covariates in the MMRM LDA models (Diggle et al., 2001).

MU-Suppression. Data will be analyzed in two ways. Pearson rank correlations will be used to examine correlations between mu wave suppression in response to a single dose of OT and symptom severity at the end of 6 weeks of treatment. In additional exploratory analyses, mu suppression values will be split at the median into High suppressors and Low suppressors and followed up by correlations with symptom measures to determine if initial high suppression is correlated with greater improvement in symptom severity. Secondarily, Pearson rank correlations will be conducted between mu wave suppression and symptom severity at baseline, and between mu wave suppression and symptom severity after administration of a single dose of oxytocin.

Safety Endpoints. The safety dataset will contain all subjects who take at least one dose of oxytocin. All adverse events will be coded using the most current version of the Medical Dictionary for Regulatory Activities (MedDRA). The number and percentage of subjects reporting treatment-emergent adverse events will be tabulated within each dose group by treatment, system organ class (SOC) and MedDRA-preferred term. Treatment-emergent adverse events will be those adverse events that begin or worsened following the first dose of study drug. Adverse events will be further classified by severity and investigator-assigned relationship to study drug.

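### Aim 7's predictor is oxytocin-induced enhancement of mu suppression, but the plan defines no pre-to-post challenge change and makes no adjustment for the pre-dose value

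*Combined protocol and SAP*

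**What the plan says.** **The aim.** Section 6 gives the seventh of its aims as follows: "To determine if oxytocin-induced enhancement of mu-rhythm suppression of 'mirror' neurons in schizophrenia patients can serve as a predictive biomarker of individual clinical response". Section 7 states the expectation that "subjects with the greatest enhancement in mu suppression are more likely to experience clinical improvement in response to 6-weeks of oxytocin treatment". Both describe a within-subject change caused by the drug.

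**The data.** Section 9, Visit 1: "Once all inclusion/exclusion criteria have been met subjects will have a baseline EEG performed". The challenge dose follows, and then the EEG paradigm again. Footnote k to the schedule also places the dose between two screening recordings, and the schedule marks two EEGs at screening and one at Visit 8.

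**The variable.** Section 9, Mu wave suppression paradigm, gives the only formula: "Mu suppression = log10 (mu power of experimental condition/ mu power of ball condition". The reference is the moving-balls video in the same session, not the pre-dose recording.

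**The analysis.** Section 9, MU-Suppression, lists first "correlations between mu wave suppression in response to a single dose of OT and symptom severity at the end of 6 weeks of treatment". Additional exploratory analyses then split the suppression values at the median and relate the groups to symptom measures, "to determine if initial high suppression is correlated with greater improvement in symptom severity". Secondary correlations relate suppression to symptom severity at baseline and after the single dose. The Missing Data paragraph refers further detail to a Statistical Analysis Plan, but for the mixed-effects model, its sensitivity analyses and its assumptions, not for the mu analysis.

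**The concern.** The aim needs a predictor that measures what the drug did to each subject. Applied as written, the formula yields how strongly a subject suppresses in one session. After the challenge, that value combines the level the subject arrived with and the effect of the dose. Section 7 reports, from a study in first-episode psychosis, that impaired suppression goes with negative symptoms and poorer social adjustment, so the arriving level may carry prognostic information of its own.

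Two things are at stake. A positive result with a level could mean that less impaired subjects do better, whatever the drug did. A true association with enhancement could be diluted and missed. In addition, with the predictor undefined, the choice between level and change could be made after the data are seen.

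**Working it through.** **Texts side by side.** Sections 6 and 7 speak of enhancement. The formula is a single-session ratio. MU-Suppression contains no post-minus-pre term and no pre-dose covariate. The one mu analysis worded in terms of improvement is the exploratory split, and it refers to initial high suppression.

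**How different are a level and a change?** The documents give no pre-post correlation, effect size or sample size for this sub-study, so there is no figure to reproduce. What follows is illustration.

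Assume equal pre- and post-dose SDs and pre-post correlation r. Then

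corr(post, post − pre) = (1 − r)/√(2(1 − r)) = √((1 − r)/2),

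and corr(pre, post − pre) has the same size with a negative sign. At r = 0.5 this is √0.25 = 0.50. At r = 0.7 it is √0.15 = 0.387.

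Assume further that enhancement correlates 0.40 with improvement, and that the level matters only through the change. The post-dose level then shows 0.40 × √((1 − r)/2). Power by Fisher z, two-sided 0.05, is Φ(atanh(ρ)·√(N − 3) − 1.96). N = 48 is the planned number on oxytocin and N = 72 the planned total.

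| r | corr(post, change) | correlation seen with post-dose level | power N = 72 | power N = 48 | median split: subjects in a different half |
|---|---|---|---|---|---|
| 0.3 | 0.59 | 0.24 | 52% | 37% | 30% |
| 0.5 | 0.50 | 0.20 | 39% | 27% | 33% |
| 0.7 | 0.39 | 0.16 | 25% | 18% | 37% |
| 0.8 | 0.32 | 0.13 | 18% | 13% | 40% |
| 0.9 | 0.22 | 0.09 | 11% | 9% | 43% |

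The last column was simulated. With the unadjusted change itself (ρ = 0.40), power is 94% at N = 72 and 81% at N = 48. If initial means the pre-dose recording, the correlation with the change runs from −0.59 to −0.22, and the split disagrees with a split on change for 70% (r = 0.3) to 57% (r = 0.9) of subjects.

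**What the pre-dose covariate does.** Write the model as Y = a + b(post − pre) + c·pre. Rearranged, Y = a + b·post + (c − b)·pre. The coefficient b and its test are identical whether the predictor is the change or the post-dose level.

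The 81% and 94% above are not the power of this adjusted model. With s² = (1 − r)/2, the partial correlation is 0.40·√(1 − s²)/√(1 − 0.16s²). At r = 0.5 it is 0.40 × 0.866/0.980 = 0.354, and at r = 0.7 it is 0.373. Using √(N − 4), power is 69% and 74% at N = 48, and 86% and 90% at N = 72.

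**Measurement error.** Suppose 0.40 is the correlation with the error-free change, single-session reliability is 0.85 and r = 0.7 (all assumed). The reliability of the difference is (0.85 − 0.70)/(1 − 0.70) = 0.50. The observed correlation is 0.40 × √0.50 = 0.28, and power at N = 48 is about 50%. The post-dose level would show 0.40 × 0.15/√0.30 = 0.11, with power about 11%. The gain is smaller, but in the same direction.

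**The case against.** A reader might infer that the plan tests a trait level instead of the drug response. The documents do not establish that. The lead correlation speaks of suppression in response to the dose. With recordings on both sides of the dose, this can fairly be read as a change, and the formula may only say how each recording is scored. Even a post-dose level contains the drug response. The sentence about initial high suppression belongs to analyses labelled exploratory, and since EEG is repeated at Visit 8, initial may mean the screening challenge as opposed to week 6.

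A reader might also take the power figures as the plan's actual loss. They are not. The correlations are assumed. N = 48 and N = 72 are ceilings, because the EEG sub-study is optional and recordings with under 2 minutes of clean data per condition are not analysed. The power calculation also assumes that the level carries no information beyond the change, whereas the worry about existing impairment assumes that it does. These are two separate scenarios, not one estimate.

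Finally, this is an optional sub-study of a self-described pilot and leaves the primary PANSS comparison untouched.

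All of this stands. It does not supply the missing definition. If a change was intended, it is nowhere written. If the formula is applied as it stands, the predictor is a level.

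**Conclusion.** The plan does not define the enhancement variable that Aim 7 requires. The lead correlation is ambiguous between post-dose level and change, the exploratory split is worded as a level, and neither adjusts for the pre-dose value.

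The choice is material. Under equal variances and r between 0.3 and 0.9, level and change share a correlation of only 0.59 to 0.22, with the sign reversed if the pre-dose level is used. The size of any loss in this trial cannot be stated from the documents.

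This should be corrected because it concerns a named specific aim, and the remedy uses data already collected.

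**What to change.** In the Mu wave suppression paradigm and MU-Suppression parts of section 9, define enhancement as the post-challenge minus the pre-challenge log10 mu ratio, for the biological-motion condition at the same sites. State that more negative means more enhancement. Use it as a continuous predictor, with the pre-challenge value as covariate, in both the lead and the exploratory Aim 7 analyses. Report the pre-challenge level separately as a marker in its own right.

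The cost is wording and one derived variable. Two limits should be stated. A difference carries error from two recordings. And because every subject receives the oxytocin challenge and no placebo challenge is described, the pre-post change can include repetition or time effects, so it is not purely drug-induced. The challenge dose is also described differently in footnote k and under Visit 1. Those two places must be reconciled, since enhancement is comparable across subjects only if the dose behind it is clear.

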- To evaluate the safety of intranasal Oxytocin as measured by reported Adverse Events
- To evaluate the safety of intranasal Oxytocin as measured by collected safety measures to include blood tests, witnessed and reported adverse events
- To evaluate changes in ability to infer the mental state of others from emotion differentiation by their performance with the Penn Emotion Recognition Test (ER-40).
- To evaluate the possible correlation between the response to intranasal Oxytocin and biological markers, specifically endogenous oxytocin levels (tested via blood and saliva sample). Using saliva to test hormone levels has become a preferred method. Many hormone levels can fluctuate throughout the day. Using saliva allows for convenient specimen collection at multiple times (ie, pre and post dose). There is a believed correlation between the "bioavailable" (or active) amount of hormone in the blood and the levels found in saliva. We will collect both blood and saliva samples to confirm or reject the proposed correlation which may lead to a more convenient way of collection in future trials. Determining hormone bioavailability is critical with hormones and saliva as the specimen medium is ideal for this.
- To assess the differential effect of oxytocin on early environment and social parameters based on scores on the Childhood Trauma Questionnaire (CTQ) and Experience Close Relationships (ECR).
- To detect and monitor any changes in sexual functioning as rated by the Arizona Sexual Experience Scale (ASEX)
- To determine if expected deficits in neural processing of socially relevant visual stimuli (mu-rhythm suppression of mirror neurons) in schizophrenia patients correlates with the severity or nature of their symptoms
- To determine if intranasal oxytocin can improve mu rhythm suppression in schizophrenia patients

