Clinical laboratory values and vital signs measured at the end of each treatment period will be analyzed using ANOVA, with factors sequence, period and treatment. Dose-response relationships will be explored and any laboratory values that fall outside normal ranges will be identified.

Missing Data. Some observations may be missing after baseline assessment. Individual missing items in all scales will not be imputed. All subjects expressing the desire to discontinue the study will be asked to come in for a final assessment, prior to stopping their medications. The primary analysis will be based on the likelihood based mixed-effects model (MMRM LDA) which provides valid estimates of treatment effect under the missing at random (MAR) assumption. The assumptions about random dropout and MAR can be tested using methods proposed by Diggle et al. (2001) and dropout cohort visualization as in Potkin et al, (2009). Two sensitivity analyses will be conducted to evaluate the robustness of results: one based on a mixed-effects model for missing not at random (MNAR) data with covariate adjustment for dropout measures (Wu and Follmann, 1999; Wu et al., 2001), and the other based on the usual LOCF-ANCOVA method with missing data following dropout imputed by an individual's last observed measurement. Further details are provided in the Statistical Analysis Plan, which will clearly specify the mixed-effects model methodology, sensitivity analyses, and evaluation of the assumptions.

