14. POTENTIAL RISKS

All medications have side effects and some of these can be unexpected and unforeseen. Subjects will be closely monitored throughout the trial duration and subjects will be provided emergency contact numbers to ensure 24-hour monitoring.

Nasal Inhalation Oxytocin

The FDA (see appended letter) notes "lack of safety concerns" associated with the clinical use of oxytocin despite ", the length of marketing history of this product in the U.S., the continued availability of the injectable oxytocin in the US and the IN form outside the US" A drug insert provided with IN nasal oxytocin in Europe where it continues to be marketed for lactation lists the following risks; painful uterine contracts; in rare occasions, allergic skin reactions, nausea or headache. Several published studies have used various doses (18- 360 IU) of IN oxytocin administered once to more than a week (e.g. Ansseau et al, 1987; Epperson 1996; Fehm-Wolfsdorf et al, 1988; Westenberg, 1992; Kosfeld et al 2005; Ruis et al, 1981; Heinrichs et al 2003; Fewtrell et al 2005; Bruins et al 1992.) Most studies do not report any adverse effects. One case (Ansseau et al, 87) of a patient developing reversible memory loss, psychosis, and a decrease in plasma sodium and osmolality is reported which is consistent with a picture of SIADH. Some studies reported decreases in verbal recall and memory whereas others did not find this. Other rare mild and transient effects were reported in some studies including, dry mouth, mild dizziness, mild headache, and mild nasal irritation. No effect on blood pressure has been noted.

Risks of Blood Draw

During the study, blood will be drawn 8 times for chemistry basic panel. Some problems from this are: pain, bleeding, bruising, swelling, dizziness, fainting, in rare cases, infection at the insertion site.

Additional Risks

Since this is an experimental treatment there may be some unknown risks that are currently unforeseeable. Subjects will be informed of any significant new findings.

Symptoms of schizophrenia may not improve or may worsen. There is also the possibility that there may be unforeseen risks associated with this test article, which are not yet known.

Allergy Risks

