15. RISK MANAGEMENT PROCEDURES AND ADEQUACY OF RESOURCES

A staff that is highly qualified in the assessment and treatment of schizophrenia in adults will closely monitor subjects in this study. This monitoring includes the frequent periodic assessments involved in the study protocol, which occur at intervals of 1 week long. Study drug will be administered on site following both baseline visits. Mid-week calls are set up following both baseline visits along with a study treatment follow up visit. In addition, subjects will be monitored throughout the study for any adverse events. Subjects will be instructed by the Investigator to report the occurrence of any adverse events immediately. At the beginning of each treatment period, the Investigator will query the subjects, in a generalized fashion, whether any clinical adverse events have occurred since the last visit. Any serious or unexpected event, including death due to any cause, whether or not related to the study drug or procedures, will be reported to the UCSD HRPP within 10 days.

After a thorough literature search was performed and confirmed the relative safety profile of this drug, the following additional safety measures were added in an attempt to be thorough.

Biological safety measures include blood chemistry and urine osmolality to monitor for SIADH. These tests will be done at screening and at every visit after randomization. In addition a blood metabolic assay (glucose, liver enzymes) will be conducted at each visit.

If any clinical worsening or serious adverse event is detected during the course of the trial that cannot be managed by a dose adjustment, the subjects will be discontinued from the protocol.

It is my intention to provide contact information for study staff to the subjects and reiterate this information at the time of each visit. Contact information for PI, and Drs. [name] and [name], are listed on the diary form that will be provided to the subject at each visit. Study subjects will be encouraged, as documented in the consent and on the separate diary form, to contact the study team with medical concerns, reactions, and experiences. Subjects will be given a diary form to complete upon each use for administrations that are done between site visits. This diary form includes 24 hour emergency contact information (including PI, sub-Is and study staff), nearest emergency department from subject's residence and concomitant medication diary.

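### The planned laboratory ANOVA uses crossover factors that this parallel trial does not have, and SIADH monitoring has no by-arm summary of low sodium or osmolality

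*Combined protocol and SAP*

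**What the plan says.** Section 9, Safety Endpoints, covers the laboratory analysis in two sentences. The first is "Clinical laboratory values and vital signs measured at the end of each treatment period will be analyzed using ANOVA", and it names sequence, period and treatment as the factors. The second is "Dose-response relationships will be explored and any laboratory values that fall outside normal ranges will be identified". No method is given for the dose-response exploration, and no count, percentage, threshold or change from screening is specified.

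The purpose of the tests is stated elsewhere. Section 15 says "Biological safety measures include blood chemistry and urine osmolality to monitor for SIADH". Section 14 gives the background: one published case in which "a decrease in plasma sodium and osmolality is reported which is consistent with a picture of SIADH". Note d to the schedule in Section 9 includes sodium and osmolality in the panel. A secondary objective in Section 6 is "To evaluate the safety of intranasal Oxytocin as measured by collected safety measures to include blood tests, witnessed and reported adverse events".

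For adverse events, by contrast, a count is planned: "The number and percentage of subjects reporting treatment-emergent adverse events will be tabulated within each dose group by treatment".

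The documents disagree on sampling. Section 15 says "These tests will be done at screening and at every visit after randomization", and Section 14 says "blood will be drawn 8 times for chemistry basic panel". The schedule table in Section 9 marks blood chemistry and urine osmolality only at Screening and at Visit 8/ET. Note b allows extra chemistry at any time if there is a health concern.

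**The concern.** There are two defects in one short paragraph.

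First, sequence and period are crossover terms. The proof-of-concept study was a crossover; this trial is not. The only laboratory method the plan names therefore does not fit the design. The same sentence governs vital signs.

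Second, a repaired version would still compare arm means. That tells the reader whether sodium shifts in most subjects. SIADH monitoring asks how many subjects in each arm had low sodium or osmolality. Aims 2 and 5 ask whether oxytocin, including 168 IU per day, is safe enough to develop further, and a reader of the results would want that number with placebo beside it. The plan promises it for adverse events and not for laboratory values. Nothing says that an out-of-range value must be recorded as an adverse event, so the adverse-event table cannot be relied on for abnormalities seen only in the laboratory.

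**Working it through.** The plan gives no figure for this analysis, so there is none to reproduce.

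**1. Does the model fit the design?** Section 9 (Overview) randomizes each subject to 84 IU/day, 168 IU/day or placebo for six weeks. Each subject has one randomized treatment and one treatment period. Period has a single level, so it cannot be estimated. Sequence has no meaning apart from the assigned arm, so it is either constant or identical to treatment. Only treatment is left, with no adjustment for the pre-treatment value.

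**2. What does a mean comparison show when few subjects are affected?** Arm size is 24 (Section 9, Sample Size Calculation). The documents give no sodium distribution. Assume an SD of 2.5 to 4 mmol/L and a fall of 10 to 15 mmol/L in an affected subject.

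- Shift in arm mean = (number affected × fall) / 24.
- One subject: 10/24 = 0.42 to 15/24 = 0.63 mmol/L.
- Two subjects: 20/24 = 0.83 to 30/24 = 1.25 mmol/L.
- Standard error of the difference between two arms = SD × √(2/24): 2.5 × 0.289 = 0.72 to 4 × 0.289 = 1.15 mmol/L.

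One marked case moves the mean by less than one standard error, so the mean does not display it.

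The mean comparison does work for a general effect. In simulation under the same SDs, a uniform 3 mmol/L fall in one arm gave p<0.05 in 72% to 98% of trials (two-sample t) or 75% to 99% (three-arm ANOVA). It should be kept.

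**3. What would a by-arm count add?** Exact (Clopper-Pearson) 95% intervals with 24 subjects:

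| Below range | 95% interval |
|---|---|
| 0/24 | 0 to 14.2% |
| 1/24 | 0.1 to 21.1% |
| 2/24 | 1.0 to 27.0% |

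Fisher's exact test against 0/24 gives p = 1.00 for one case and 2 × C(24,2)/C(48,2) = 552/1128 = 0.49 for two. It first falls below 0.05 at five cases: 2 × C(24,5)/C(48,5) = 85,008/1,712,304 = 0.0496. The table describes; it does not test.

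**4. Background.** Assume a mean of 140 and a lower limit of 135 mmol/L. The expected number of 24 untreated subjects below range on one sample is 24 × Φ(−5/SD): 24 × Φ(−2) = 0.5 for SD 2.5, up to 24 × Φ(−1.25) = 2.5 for SD 4. On the lowest of six samples (within-subject correlation 0.5 to 0.7) it is 1.8 to 8.0. A count without the placebo column and the number of samples per subject would mislead.

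**5. Sampling.** Screening, Baseline and Visits 3 to 8 make 1 + 1 + 6 = 8 clinic visits, which agrees with the eight draws in Section 14. The schedule table gives two. The documents do not settle which applies.

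**The case against.** The strongest case against is that little is missing. The out-of-range clause covers any value, not only end-of-period ones, so low sodiums would be found whenever drawn. With 24 per arm, counting them by arm is one cross-tabulation. Symptomatic cases would probably reach the adverse-event table. The trial is a pilot, and a statistician would drop the two impossible factors without being told. Much of this stands, and it is why the point is minor. What remains is that the written model is wrong, and that finding individual values is not the same as committing to an incidence by arm.

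Three stronger readings are tempting, and none is supported.

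- **That SIADH cases would be hidden.** They would not; the plan identifies out-of-range values.
- **That a count would detect a difference where the mean test fails.** By that yardstick the count does worse. Under the assumptions above (falls of 10 to 15 mmol/L, one sample), simulation gave p<0.05 by Fisher's test in 0.1% to 2.2% of trials with one case and in under 5% with two. The mean tests gave 4.2% to 5.0% and 7.1% to 10.4%.
- **That the analysis discards weeks 1 to 5, or misses falls that recover.** The first needs weekly chemistry, which Sections 14 and 15 suggest but the schedule table contradicts. The second also needs sodium to recover while dosing continues, which nothing in the documents supports.

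**Conclusion.** The point holds in two parts. The laboratory ANOVA cannot be run as written, because sequence and period are not features of this design; that follows from the text alone. As a mean comparison it also leaves the SIADH question without a by-arm summary. The size given for the second part (a shift of 0.42 to 0.63 mmol/L for one case in 24) rests on an assumed fall of 10 to 15 mmol/L. The comparison with sampling error rests on an assumed SD of 2.5 to 4 mmol/L.

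The added table has descriptive value only. If the Section 9 schedule governs, most subjects have a single post-dose sample, and the table mainly contributes the by-arm count and the change from screening. Severity is minor: no efficacy conclusion, error rate or sample size is affected.

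**What to change.** Replace the ANOVA sentence with an ANCOVA of the end-of-treatment value on treatment arm (placebo, 84 IU, 168 IU), with the screening value as covariate. Screening is the only pre-treatment chemistry in the schedule table. Remove sequence and period for vital signs as well.

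Add one descriptive table by arm, placebo included, for serum sodium and serum osmolality:

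- lowest post-dose value per subject;
- largest fall from screening;
- n/N below the laboratory's normal range with exact 95% interval, where N is subjects with at least one post-dose sample;
- number of post-dose samples per subject.

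Use all samples after the first randomized dose: scheduled, early-termination and unscheduled. State that placebo subjects belong to the safety set, because Safety Endpoints defines that set by a dose of oxytocin while Analysis Methods refers to study medication.

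The cost is a wording change and one table, with no new samples. The drawbacks are wide intervals and some below-range values unrelated to drug, which the placebo column and the sample counts help the reader judge.
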